TRPL	Tear film rupture time
SLG	Staining with Lysmine Green
UFTLS	Pharmacovigilance and Technovigilance Unit of Sophia Laboratories
CV	Current version
x ²	Chi-square
°C	Celsius degrees

1. Protocol Summary

1.1 Synopsis

Title of the study: Phase I clinical study, to evaluate the safety and tolerability of the PRO-201 ophthalmic solution, prepared by Laboratorios Sophia, S.A. de C.V. on the ocular surface of ophthalmologically and clinically healthy subjects	
Study Number: SOPH201-0521/I	Date of creation: 28/May/2021
Protocol version: 1.0	Release Date: Aug/10/2021
Therapeutic indication: Adjuvant in treatment to delay the progression of myopia.	Use: Myopia
Estimated duration of the study (from the first visit of the first patient to the preparation of the final report): 6 months	Clinical Development Phase: I
Objectives: Main objective: 
• To evaluate the safety and tolerability of the PRO-201 formulation manufactured by Laboratorios Sophia S.A. de C.V. on the ocular surface of ophthalmologically and clinically healthy subjects. Specific objectives: 
• Primary
○ To evaluate the safety of PRO-201 ophthalmic solution applied to the ocular surface in healthy volunteers, through the incidence of unexpected adverse events (AEs) related to the investigational product (PI).	

[figure not shown]

 ○ To assess the tolerability of PRO-201 ophthalmic solution applied to the ocular surface in healthy volunteers using the incidence of photophobia. ● Secondary 
 ○ To evaluate the safety of PRO-201 ophthalmic solution applied to the ocular surface in healthy volunteers, by evaluating the pupillary diameter by the OPD scan. ○ To evaluate the safety of PRO-201 ophthalmic solution applied to the ocular surface in healthy volunteers, using the incidence of expected PI-related AEs. ○ To evaluate the tolerability of PRO-201 ophthalmic solution applied to the ocular surface in healthy volunteers, by evaluating the best corrected near visual acuity (CVA) with the ETDRS primer. ● Exploratory 
 ○ To assess the safety of PRO-201 ophthalmic solution applied to the ocular surface in healthy volunteers, by assessing best-corrected visual acuity (BCVA). ○ To evaluate the safety of PRO-201 ophthalmic solution applied to the ocular surface in healthy volunteers, by assessing intraocular pressure (IOP). ○ To evaluate the safety of PRO-201 ophthalmic solution applied to the ocular surface in healthy volunteers, by evaluating corneal and conjunctival staining with fluorescein and lysmine green. ○ To assess the safety of PRO-201 ophthalmic solution applied to the ocular surface in healthy volunteers, by assessing vital signs (heart rate and blood pressure). ○ To evaluate the tolerability of PRO-201 ophthalmic solution by means of the Ocular Comfort Index (ILO) score.

Hypothesis:
 
H0= The PRO-201 ophthalmic solution is not safe in its ophthalmic application as it has an incidence of unexpectedly related adverse events (AEs) greater than 10% and is not tolerable as it presents an incidence of photophobia greater than 15% of the study population.
 $H_0: p - p_0 \leq -\delta$ 
H1= PRO-201 ophthalmic solution is safe in ophthalmic application with an incidence of unexpected, related adverse events (AEs) of less than 10% and is tolerable with an incidence of photophobia of less than 15% of the study population.
 $H_1: p - p_0 > -\delta$

Study Design:
 
Phase I Clinical Trial, Controlled, Non-Comparative, Open-label, Single-Center

Number of subjects (planned and analyzed):

Number of planned subjects: 29 evaluable subjects (both eyes)
Diagnosis and main inclusion criteria: - Ophthalmologically and clinically healthy subjects.
Selection criteria:
Inclusion criteria: 
- Be clinically healthy- Can voluntarily give their signed informed consent (CRF)- Be able and willing to comply with scheduled visits, treatment plan, and other study procedures- Be between 18 and 35 years old.- No history of contact lens use- Women of childbearing potential must ensure continued use (initiated \geq 30 days prior to signing the CRF) of hormonal contraceptive or intrauterine device (IUD) use during the study period- Have a better far-corrected visual acuity of 20/30 (logMAR 0.2) or better in both eyes.- Have a better corrected visual acuity close to 20/25 (logMAR 0.1) or better in both eyes.- Have vital signs within normal parameters.- Have an IOP \geq10 and \leq 21 mmHg.
Exclusion criteria: 
- Be a user of topical ophthalmic products of any kind.- Allergy or known intolerance to ingredients in atropine eye drops and other derivatives of muscarinic antireceptor agents.- Being a user of medicines, or herbal products (plant extracts, infusions, naturopathic preparations, homeopathics, etc.), by any other means of administration.- For women: being pregnant, breastfeeding, or planning to become pregnant within the study period.- Have participated in any investigational clinical study 90 days prior to inclusion in the present study.- Have previously participated in this same study.- Who are unable to follow the lifestyle considerations described in Annex 1.- Have a history of any chronic-degenerative disease, including diabetes and high blood pressure.- Have an active inflammatory or infectious disease at the time of study entry.- Have unresolved injuries or trauma at the time of study entry.- Have a history of any type of eye surgery.- Having undergone surgical, non-ophthalmologic procedures within the past 3 months.- Be or have an immediate family member (e.g., spouse, parent/legal guardian, sibling, or child) who is employed by the research site or sponsor, and who is directly involved in this study.


Elimination criteria:
 
 – Withdrawal of the letter from the FCI. – Presentation of a serious adverse event related or not to the investigational product, which at the discretion of the PI and/or sponsor could affect the patient's ability to continue with the study procedures safely. – Non-tolerability or hypersensitivity to any of the compounds used during the tests (fluorescein, lysmine green, tetracaine). – No tolerability or hypersensitivity to the investigational drug. – Adherence < 90% determined by the subject's diary 	

Research Product (PI):
 
 - PRO-201 . Atropine Sulfate 0.01%. Zapopan, Jalisco, Mexico. Ophthalmic solution Laboratorios Sophia, S.A. de C.V - Dosage: 1 drop once a day (QD) in the evening, in both eyes (AO). - Route of administration: Ophthalmic 	

Duration of treatment: 14 days
	
Duration of the subject in the study: 21 days

Evaluation criteria:
 
Primary outcome variables
 
 – Incidence of unexpected PI-related AEs (Time of Assessment [TE]: days 7, 16 and 21) – Incidence of IP-related photophobia. (TE: 7th, 16th and 21st) 
Secondary outcome variables:
 
 – Changes in pupillary diameter (ET: day 7 and 16). – Incidence of expected PI-related AEs (TE: days 7, 16, and 21). – Changes in visual acuity (TE: day 7 and 16). 
Exploratory variables:
 
 – Changes in the AVMC (TE: day 7 and 16). – Intraocular pressure (IOP) changes (ET: day 7 and 16). – Changes in corneal and conjunctival staining with fluorescein and lysmine green (ET: day 7 and 16). – Changes in vital signs (heart rate and blood pressure) (ET: day 7 and 16). – Changes in the OCI (TE: day 16). 	

Statistical methodology
 
The analysis of the data collected in the study will be carried out using the SPSS version 19.0 statistical package. For continuous and discrete quantitative variables, data will be expressed by
	

measures of central tendency: mean, standard deviation, and ranges. Qualitative data will be presented as frequencies and percentages. The statistical analysis to rule out differences will be carried out by means of non-parametric statistics. The Kolmogorov-Smirnov statistic will be used for a sample and the Mann-Whitney statistic (when applicable). The analysis for qualitative variables will be performed by means of Pearson's χ^2 (Chi-square) test or Fisher's Exact test (when applicable). For all analyses, a $p < 0.05$ and an alpha of 0.05 (two-tailed) will be considered significant.

1.2 Study diagram

BV= Basal visit

VF= Final visit. Evaluation of outcome variables.

QD= Once a day

In parentheses () is the allowed window period.

V1 = Visit 1

SC = Safety Call

AO= Both eyes

CONFIDENCIAL

1.3 Subject Timeline

Procedures	VB	V1	VF	SC
	D 1	D 7 ± 1	D 16 ± 1	D21 ± 1
Informed Consent Form (FCI) Signature	X			
Medical history	X			
Eligibility Criteria	X			
Concomitant Drug Evaluation	X	X	X	
Urine pregnancy test	X		X	
Vitals signs	X	X	X	
Best Corrected Visual Acuity (BCVA)	X	X	X	
Best Corrected Near Visual Acuity (BCNVA)	X	X	X	
Pupillary diameter measurement	X	X	X	
Evaluation of fluorescein staining and lysmine green	X	X	X	
PIO	X	X	X	
Comprehensive ophthalmological evaluation	X	X	X	
Adverse Event (AE) Assessment	X	X	X	X
Subject Code Assignment and Research Product (PI)	X			
Eye Comfort Index (ECI)	X		X	
Delivery of the PI and initiation of intervention	X			
Daily subject delivery	X			
Adherence assessment		X	X	
Return / evaluation of the subject's diary			X	
Return of PI			X	

2. Introduction and background

2.1 Theoretical framework

Myopia is a refractive error of the eye in which light rays converge on a focal point in front of the retina, instead of converging on the retina itself, making it difficult to focus well on distant objects. In progressive myopia, this defect occurs due to an exaggerated growth of the eyeball that causes a progressive thinning of all layers of the eye, with the retina being the most affected. [1]

Myopia is one of the five priorities for the World Health Organization (WHO) in the initiative "Vision 2020: The Right to Sight" [2]. It is estimated that half of the world's population will be myopic by 2050. [3]

Although the exact etiology of myopia remains difficult to explain, it appears to have both genetic and environmental components, making prevention and treatment challenging and individualized. Stopping the progression of myopia has the potential to positively affect quality of life and eye health. [4]

The initial problem with myopia is that patients who suffer from it do not see far away, but what is really important Limiting the progression of myopia is explained by the increased risk of blindness with ≤ -6 diopters and/or ≥ 26 mm axial length (macular neovascular membrane, macular chorioretinal atrophy, retinal detachments, glaucoma, etc.). [5] [6]

Myopia usually appears between the ages of six and eight and progresses on average diopter per year until the age of 15 or 16, but there are patients who continue to increase for practically their entire lives. [1]

We are facing an increase in myopia globally; in the United States of America, 42% of the population is myopic, a percentage that in 1970 was 25%. In some areas of Asia such as Taiwan, Singapore, and Hong Kong, young adults have myopia rates of 80 to 90%. [7]

There are different studies that show that the most effective way to slow down the progression of this type of myopia is the use of topical antimuscarinic drugs. Among the antimuscarinic drugs, atropine eye drops have been confirmed to be the safest and most effective treatment. [8]

Atropine is the most studied and used non-selective antimuscarinic agent to stop the progression of myopia. The first references, in German and English publications, to the use of atropine in the treatment of myopia date back to the 1970s in the 1970s. [9, 10]

The ATOM studies (for its acronym in English *Atropine for the Treatment of Myopia*) they have used atropine in different concentrations (1%, 0.5%, 0.1% and 0.01%) for a period of up to 5 years, demonstrating a reduction in the progression of myopia; as well as in the increase of axial length. Finding a small percentage of adverse effects in the population studied. [11, 12, 13, 14]

The effect of decreasing the progression of myopic refractive error using 0.01% atropine is currently recognized. However, today 0.01% atropine is only marketed in Asia and magisterial preparations are made in American countries such as Canada. In clinical trials, patients are provided with dilutions prepared with artificial tears. Although there are ophthalmologists who make this dilution in their clinics, this practice can present risks of dosage, stability and asepsis if it is not carried out under adequate conditions. [15]

2.2 Background on the investigational product

We do not have clinical studies of an ophthalmic solution containing 0.01% atropine sulfate so far. However, we have the experience in clinical studies with atropine sulfate at concentrations higher than PRO-201.

2.2.1 Preclinical study to evaluate the feasibility of a 1.0% atropine sulfate-induced model of dry eye in albino rabbits New Zealand

Fifteen healthy New Zealand albino rabbits were given a 1% atropine sulfate solution three times daily for 14 days in both eyes, and five other rabbits served as a control group, as part of a preclinical study to evaluate the feasibility of a dry eye model. In the results of the study regarding the histopathological analysis of eyeballs, all the results of the 40 eyes studied were within normal limits, finding only slight changes such as those related to tissue preservation/fixation and no evidence of any pathological alteration. This is relevant because, together with the IOP levels evaluated (found within normal parameters) and the absence of AEs reported in this study, the histopathological result confirms the safety profile of the currently marketed product. [16]

2.2.2 Clinical study of safety, tolerance and mydriatic efficacy of a topical ophthalmic reformulation of 1% atropine sulfate

Open-label, single-center, observational, prospective clinical study included thirty healthy volunteers. The volunteers administered a drop of 1% atropine sulfate in reformulation once a day in a single dose and in only one eye, and the effect was assessed one hour after application. Biomicroscopy was performed at baseline and one hour after application, evaluating the presence or not of conjunctival hyperemia, conjunctival secretion, ciliary injection, chemosis, and corneal surface, as well as Rose Bengal and Fluorescein stains, grading on a scale of 0= absent, 1= mild, 2= moderate, and 3= severe, according to the staining of the ocular surface and the pupillary diameter, both horizontally and vertically. Of the 30 patients included in this study, there was no presence of drug residues or significant alterations of the conjunctival surface.

Regarding mydriatic efficacy, pupillary dilation of up to twice the basal size was observed, both in the vertical diameter and the horizontal diameter. Regarding tolerance and safety, only 9 patients (30%) reported mild burning, with an average of 0.3 on a scale of 0 to 3. In the same area, there was also no uptake of fluorescein or Rose Bengal on the ocular surface. Based on the results presented, it can be concluded that 1% atropine sulfate (Atro Ofteno®) in reformulation has a good mydriatic efficacy

one hour after its application, as well as being safe and well tolerated when applied to the ocular surface of healthy volunteer patients. [17]

2.3 Background on the investigation

2.3.1 From the research question

Is the application of PRO-201 ophthalmic solution safe and tolerable in clinically healthy subjects?

The importance of the question that precedes this paragraph is that Laboratorios Sophia S.A. de C.V. does not have clinical studies with products identical to the PRO-201 solution, although there are with similar products (different concentration and excipients).

2.4 Risk-benefit assessment

2.4.1 Known potential risks

Formulations containing atropine sulfate at the same concentrations as PRO-201 are products that are marketed in Asia, as well as in compounding formulations in other countries in the Americas and Europe. The risks of using this product in specific populations are described below, however, the use of this drug in the study will be in a population group without the alterations or characteristics described below. To Concentration at 0.01% The potential risks are: photophobia, mydriasis, difficulty reading, allergic eye reactions (atopic dermatitis, allergic conjunctivitis and other allergic reactions), eye irritation, burning eyes, eye pain, tearing, foreign body sensation, dry eye, hyperemia and/or red eye, blurred vision, eye itching; Systemic adverse events include: headache, drowsiness, dizziness, tachycardia, flushing, restlessness, irritability, dry skin, dry mouth, skin rash and decreased alertness. [8] [6] [18] [19] [20] [21] [22] [23] [24]

2.4.2 Known potential benefits

The benefit in the target population is to serve as an adjuvant in the treatment to delay the progression of myopia. But for the study population, as it is a phase I study, it will be a healthy population. Therefore, a direct benefit for each individual is not expected, and the benefit provided by the research will be the [11, 12, 13, 14, 25] to know the behavior of the formulation; Have more data on their safety to be able to prevent or warn of unwanted effects on users or problems with their tolerance.

2.5 Problem statement

The effect of decreasing the progression of myopic refractive error using 0.01% atropine is currently recognized. However, today 0.01% atropine is only marketed in Asia and magisterial preparations are made in American countries such as Canada. In clinical trials, patients are provided with dilutions prepared with artificial tears. Although there are ophthalmologists who make this dilution in their clinics, this practice can present risks of dosage, stability and asepsis if it is not carried out under adequate conditions. [15]

Therefore, the development of a 0.01% atropine solution manufactured and marketed by Laboratorios Sophia, S.A. de C.V., would represent a great opportunity as a treatment to prevent progression in the face of the increase in myopia cases worldwide that has been recorded in recent years.

The Laboratory has experience in preclinical and clinical studies with products with 1% atropine, as well as experience in commercialization. However, having no experience with the formulation of PRO-201, it is important to develop the appropriate clinical research.

2.6 Rationale for the study

Laboratorios Sophia, S.A. de C.V., has carried out preclinical and phase I clinical studies of a similar formulation, but with a higher concentration of the component. The decrease in the concentration of the main component (atropine sulfate) in the PRO-201 solution to this formulation studied could mean a greater safety of PRO-201, not necessarily a greater tolerance, since the excipients may be involved with clinical manifestations unrelated to the main components.

Therefore, the present study serves to test the safety and tolerability of the PRO-201 product, in a controlled environment with healthy subjects.

3. Objectives and hypotheses

3.1 Objectives

3.1.1 Main objective:

- To evaluate the safety and tolerability of the PRO-201 formulation manufactured by Laboratorios Sophia S.A. de C.V. on the ocular surface of ophthalmologically and clinically healthy subjects.

3.1.2 Specific objectives:

3.1.2.1 Primary

- To evaluate the safety of PRO-201 ophthalmic solution applied to the ocular surface in healthy volunteers, through the incidence of unexpected adverse events (AEs) related to the investigational product (PI).
- To assess the tolerability of PRO-201 ophthalmic solution applied to the ocular surface in healthy volunteers using the incidence of photophobia.

3.1.2.2 Secondary

- To evaluate the safety of PRO-201 ophthalmic solution applied to the ocular surface in healthy volunteers, by evaluating the pupillary diameter by the OPD scan.
- To evaluate the safety of PRO-201 ophthalmic solution applied to the ocular surface in healthy volunteers, using the incidence of expected PI-related AEs.
- To evaluate the tolerability of PRO-201 ophthalmic solution applied to the ocular surface in healthy volunteers, by evaluating the best corrected near visual acuity (CVA) with the ETDRS primer.

3.1.2.3 Exploratory

- To assess the safety of PRO-201 ophthalmic solution applied to the ocular surface in healthy volunteers, by assessing best-corrected visual acuity (BCVA).
- To evaluate the safety of PRO-201 ophthalmic solution applied to the ocular surface in healthy volunteers, by assessing intraocular pressure (IOP).
- To evaluate the safety of PRO-201 ophthalmic solution applied to the ocular surface in healthy volunteers, by evaluating corneal and conjunctival staining with fluorescein and lysmine green.
- To assess the safety of PRO-201 ophthalmic solution applied to the ocular surface in healthy volunteers, by assessing vital signs (heart rate and blood pressure).
- To evaluate the tolerability of PRO-201 ophthalmic solution by means of the Ocular Comfort Index (OCI) score.

3.2 Hypothesis

H0= The PRO-201 ophthalmic solution is not safe in its ophthalmic application as it has an incidence of unexpectedly related adverse events (AEs) greater than 10% and is not tolerable as it presents an incidence of photophobia greater than 15% of the study population.

$$H_0: p - p_0 \leq -\delta$$

H1= PRO-201 ophthalmic solution is safe in ophthalmic application with an incidence of unexpected, related adverse events (AEs) of less than 10% and is tolerable with an incidence of photophobia of less than 15% of the study population.

$$H_1: p - p_0 > -\delta$$

4. Study design

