7.4 Outcome variables

7.4.1 Primary outcome variables

- Incidence of unexpected PI-related AEs.
- Incidence of IP-related photophobia.

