10.1.2 Size Calculation

The PRO-201 ophthalmic solution is expected to be safe in its ophthalmic application when it has an incidence of unexpected, related AEs of less than 10%, and is tolerable when it has an incidence of photophobia that is less than 15% of the study population.

On this basis, a sample of 24 ophthalmologically and clinically healthy subjects was estimated. This value was increased by 20% considering possible losses. Based on this consideration, 29 subjects (who will contribute one eye, OD) are required to respond to the primary objective of the study.

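### The primary null hypothesis is not the complement of the alternative: a result that meets one limit and misses the other belongs to neither, and the plan does not say how to classify it

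*Combined protocol and SAP*

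**What the plan says.** Section 7.4.1 lists two primary outcome variables: "Incidence of unexpected PI-related AEs" and "Incidence of IP-related photophobia". Section 3.2, repeated in the synopsis (1.1), covers both with one null and one alternative.

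- **Null.** The product is not safe, on account of "an incidence of unexpectedly related adverse events (AEs) greater than 10% and is not tolerable as it presents an incidence of photophobia greater than 15" per cent.
- **Alternative.** The product is safe with an incidence of unexpected related adverse events "of less than 10% and is tolerable with an incidence of photophobia of less than 15% of the study population".

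The symbolic versions use one p, one p0 and one delta. They give no values and no index by endpoint, so they do not settle the structure.

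Section 10.1.2 repeats the success limits: the product is taken as safe when the adverse-event incidence is "less than 10%, and is tolerable when it has an incidence of photophobia that is less than 15% of the study population". Board 1 in 7.4.4 gives each variable its own reference value, below 10% and below 15%.

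Section 10.3.2.1 names Kolmogorov-Smirnov, Mann-Whitney and chi-square or Fisher tests. It does not compare either incidence with its limit, and it gives no rule for combining the two results.

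On error level, the synopsis states that "an alpha of 0.05 (two-tailed) will be considered significant". The sample-size table in Annex 16.5 is for one-sided 0.05 with target power 0.80.

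**The concern.** A test supports its alternative only if ruling out the null leaves nothing but the alternative. Here the null is that both incidences are too high. Its negation is that at least one of them is not above its limit, which is much weaker than the alternative that both are below their limits. A low photophobia rate alone would contradict the null as written while saying nothing about unexpected related adverse events.

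At stake is what the primary conclusion means in a foreseeable case: one endpoint inside its limit and the other outside. Under the literal null, that result is evidence against H0. Under the literal alternative, H1 is not met. If the sentence is read as two separate questions, one is answered yes and the other no. The plan does not choose among these.

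**Working it through.** **1. Logic of the hypotheses (3.2 and 1.1).** The two limits divide the possibilities into four.

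| Unexpected related AE incidence | Photophobia incidence | Hypothesis as written |
|---|---|---|
| above 10% | above 15% | H0 |
| below 10% | below 15% | H1 |
| above 10% | below 15% | neither |
| below 10% | above 15% | neither |

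Exact equality at 10% or 15% is also unassigned in the wording. This step does not depend on sample size, alpha or choice of test. The complement of H1 is: AE incidence at least 10% **or** photophobia at least 15%.

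**2. The plan's own figure.** Section 10.1.2 starts from 24 subjects and adds 20%: 24 × 1.20 = 28.8, rounded to 29. That step reproduces. The base of 24 could not be reproduced from the limits or from Annex 16.5, but the logical point does not need it.

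**3. What the restated null would require.** The plan contains no test against 10% or 15%, so an exact one-sided binomial test is my assumption. The p-value is P(X ≤ x | n, p0); with no events it is (1 − p0)^n.

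| n, events | Against 10% (AE) | Against 15% (photophobia) |
|---|---|---|
| 29, none | 0.90^29 = 0.0471 | 0.85^29 = 0.0090 |
| 29, one | 0.1989 | 0.0549 |
| 24, none | 0.90^24 = 0.0798 | 0.85^24 = 0.0202 |

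- One-sided 0.05, n = 29: each component can be rejected only with zero events.
- 0.025 in the relevant tail (two-tailed 0.05), n = 29: the AE component cannot be rejected even with zero events, since 0.0471 > 0.025. The joint claim is unreachable.
- n = 24 (the base number before inflation): the AE component cannot be rejected at either level, since 0.0798 > 0.05.

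**4. Error of requiring both, one-sided 0.05, n = 29.** Both rejections together cannot be more probable than either one alone. If the AE incidence is at least 10%, the joint claim has probability at most 0.0471. If photophobia is at least 15%, it is at most 0.0090. The maximum is 0.0471 whatever the dependence, so no alpha split is needed (intersection-union principle).

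**5. Power of requiring both, one-sided 0.05, n = 29.** The true rates are assumptions.

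- AE 1%, photophobia 2%: 0.99^29 = 0.7472 and 0.98^29 = 0.5566. Under independence the product is 0.416.
- Without independence, the same rates allow from 0.7472 + 0.5566 − 1 = 0.304 up to 0.557.
- AE 2%, photophobia 2%: 0.5566 × 0.5566 = 0.310 under independence.
- AE 5%, photophobia 2%: 0.2259 × 0.5566 = 0.126 under independence.

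**The case against.** The best defence is that each verdict is paired with its own reason: not safe because of adverse events, not tolerable because of photophobia. Read as two parallel questions, each pair is complementary except at equality. The text also reads as a translation, so one conjunction is weak evidence of intent. Sections 3.1.2.1, 7.4.4 and 10.1.2 tie safety to one variable and tolerability to the other, and both H1 and 10.1.2 already join the two successes with 'and'.

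Much of this stands. The two-question reading is possible and may be what was meant. But the text is one H0 and one H1, no section states the parallel reading, and the readings classify a mixed result differently.

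A reader might go further and infer that the plan lets the product be called safe and tolerable through the easier endpoint. The documents do not support that. H1, the only positive claim, needs both, and no section sets a test that could reject on photophobia alone. The literal null would permit that inference, but the plan does not state it.

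A reader might also take 0.98^29 = 0.557 as the chance of a false joint claim. It is only the chance of rejecting the photophobia half at a true rate of 2%. If both are required, with an assumed true AE rate of 20% and independence, the false joint claim has probability 0.80^29 × 0.98^29 = 0.00155 × 0.557 = 0.0009 by exact tests, or about 0.052 if the observed rates are simply compared with the limits. Nor is 2% photophobia this trial's stated expectation: section 10.1.1 cites it from a review of treated children, and this trial enrols adults aged 18 to 35. It serves here only as an assumed value.

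**Conclusion.** The point holds as a defect in the stated primary hypothesis. H0 and H1 in 1.1 and 3.2 are not complements, mixed states belong to neither, and no section says how a mixed result is classified. This is a matter of logic and needs no assumption. It does not show that the sponsor intends to claim success on one endpoint.

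The figures measure the cost of a properly stated hypothesis, not a false-claim rate under the present text. They rest on an exact binomial test that the plan does not contain. The zero-event thresholds and the 0.0471 ceiling need nothing more; the joint power of about 0.42 also needs true rates of 1% and 2% and independence. The case of 24 subjects is a scenario: the primary analysis includes everyone who received a dose, and 5.2.2 allows replacement, so 29 may be kept.

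**What to change.** 1. In 1.1 and 3.2, restate H0 as the complement of H1: unexpected related AE incidence at least 10%, **or** photophobia incidence at least 15%.
2. In 10.3.2.1, state that the product is concluded to be both safe and tolerable only if both components are met, each assessed at the full named level with no alpha split. If only one is met, report that component alone as met and the overall hypothesis as not met.
3. Name the alpha and sidedness for each component. The synopsis (two-tailed 0.05) and Annex 16.5 (one-sided 0.05, for a time-to-event design taken from a publication) differ, and with 29 subjects the choice decides whether the joint claim can be reached.
4. Disclose the consequence for an exact test: unreachable at 0.025 in the relevant tail; zero events in 29 on both endpoints at one-sided 0.05, with joint power of about 0.42 at the assumed rates; AE limit not rejectable with 24 subjects.

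Items 1 to 3 are wording changes and need no new data. The cost is not small in another sense: correctly stated, the joint claim is hard to reach with 29 subjects, and the sponsor should settle whether that is acceptable before seeing data.
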